### **3.3 Breaking the blind**

Unblinding of subjects will be limited to reduce the potential for bias. Unblinding of a subject will only be considered in cases in which there is a significant safety or health concern to the subject and only after consultation with the treating physician, the study Medical Director ([name] MD) and Principal Investigator ([name]). Only those individuals who need to know the subject's group assignment to ensure the health and safety of the subject will be unblinded. To the extent possible, all of the other study staff will remain blinded to the subject's group assignment.

A statement will be placed in the electronic medical record of the subject stating the subject is enrolled in a double-blinded placebo controlled trial using losartan potassium as an investigational drug. In the event of a medical emergency, a health care provider can contact the study Medical Director or other designated study investigator to obtain information about the assigned study drug during the dosing period.

If unblinding becomes necessary, the following information will be recorded:

- Randomization identification number of the unblinded subject;
- Reason for unblinding;
- Study staff member that is responsible for unblinding the subject and
- A list of person(s) who are not blinded.

## **4. Subject Selection:**

Subjects will be drawn from the population of patients with an acute grade II or grade III hamstring injury that present to the UPMC Center for Sports Medicine or Athletic Training Rooms at the University of Pittsburgh or to the Brooke Army Medical Center. A total of 20 subjects will be enrolled in the study. A subject will consider to be enrolled in the study if he/she has provided informed consent for study participation.

#### **4.1 Subject inclusion criteria**

Subjects will be eligible for participation in this study if they are between 18 and 35 years of age and if they have had a grade II or III hamstring injury in the previous 7 days of enrolling in the study. Only those individuals who are regular participants (greater than 100 hours per year) in Level I (football, basketball or soccer) or Level II (racquet sports, skiing, manual labour occupations/heavy physical work) activities will be eligible for participation in this study. Individuals from BAMC that suffer a grade II or III hamstring injury in the previous 7 days of enrolling in the study that are involved in military training that at least is equivalent to heavy physical work in the civilian subjects will be eligible to participate in the study. To be eligible to participate in the study, subjects will need to agree to take the study medications as prescribed.

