## 1.2 Rationale:

Developed in 1990, losartan potassium is an FDA-approved drug for the treatment of hypertension, left ventricular hypertrophy and diabetic nephropathy. Losartan and EXP3174 have been referenced in 184 studies according to PubMed (United States Library of Medicine). These reports have shown losartan is a specific blocker of the type-1 angiotensin II receptor, which regulates the expression of TGF- $\beta$ 1. Our research shows strong expression of TGF- $\beta$ 1 in injured skeletal muscle, which clearly implicates TGF- $\beta$ 1 in the fibrotic cascade that occurs after the onset of muscle disease or trauma. Indeed, the use of anti-fibrotic agents that inactivate TGF- $\beta$ 1 reduce muscle fibrosis, improves muscle healing and leads to enhanced recovery of injured muscle. Losartan potassium (MerckTM) is an FDA approved drug whose use has been associated with a reduction in fibrosis in several tissues. Furthermore, it has been used to improve myoblast transplantation and protect against sarcopenia.

Based on our promising experimental data in a murine muscle injury model, the goal of this phase 1 randomized double blind placebo-controlled clinical trial is to test the effects of Losartan on muscle healing after sports, military training or combat injuries. Muscle injury caused by vigorous physical activity occurs in the US Active Duty Army at rates 3 to 4 fold higher than the civilian population. Subject recruitment will include athletes or military personnel, veterans or their families that have sustained an acute sports-related hamstring injury. This is relevant to the injured military population, since advances in combat field medicine translates into high rates of survival and increased numbers of wounded warriors, with the majority of injuries occurring in the upper and lower extremities.

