### **5.5.2 Rescue Medication**

## **6. Research Study Procedures:**

### **6.1 Recruitment Procedures**

This prospective randomized phase 1 trial is a joint effort of the UPMC Center for Sports Medicine/University of Pittsburgh and the Department of Orthopaedics and Rehabilitation at BAMC.

Subjects recruited through the UPMC Center for Sports Medicine will be informed of and referred to the study by their athletic trainer and/or physician. With permission of the subject, a research assistant will then contact them and initiate the study process. Alternatively, potential subjects will sign a Health Insurance Portability and Accountability Act (HIPAA) authorization for sharing of contact information, which will be forwarded to the study coordinator, who will in turn contact the subject to provide additional information concerning the study.

Subjects recruited through the Department of Orthopaedics and Rehabilitation at Brooke Army Medical Center (BAMC) in San Antonio, Texas that meet the inclusion criteria (grade II/III hamstring strains due to sports or duty related injury) will be referred to the Research Coordinator in the BAMC Department of Orthopaedics and Rehabilitation for possible recruitment. All testing and evaluation of recruited subjects will be conducted at the Center for the Intrepid in the Department of Orthopaedics and Rehabilitation at BAMC,

MRI's will be performed at the BAMC Department of Orthopaedics and Rehabilitation MRI Clinic.

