### **6.4.2.1 Return to Previous Level of Sports Activity and Recurrence of Injury (Specific Aims 3 and 4)**

The primary outcome for return to sports will be the number of days from injury to full, unrestricted return to practice or military training. The secondary outcome for level of sports activity will be the Marx Activity Scale Score. At 4 and 6 weeks, the Marx Sports Activity Scale will be modified to measure sports activity in the last week and at 4, 6 and 12 months the scale will be modified to measure sports activity in the past month.

Recurrence of injury will be monitored over the course of 12 months after study enrolment and randomization. A subject will be considered to have a recurrent injury if there was a specific mechanism of injury that caused a return of posterior thigh pain, tenderness to palpation along the muscle-tendon unit, pain with resisted knee flexion and the inability to participate in sports activities. Recurrent injuries will be monitored weekly during the course of rehabilitation and at each follow-up study visit (1, 2, 3, 4 & 6 weeks, 6 months) and follow-up phone call (3, 4, 9 and 12 months). After return to sports participation, any subject experiencing a recurrent injury will be instructed to contact the Project Coordinator and a return visit will be scheduled to confirm the presence and severity of re-injury.

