#### **Specific Aim #3: Time to Return to Prior Level of Function**

The primary outcome for return to sports will be the number of days from injury to full, unrestricted return to practice.

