#### **Specific Aim #4: Recurrence of Injury**

The primary outcome for recurrence of injury will be the incidence of recurrent injury. A recurrent injury will be considered to have occurred if there was a specific mechanism of injury that caused a return of posterior thigh pain, tenderness to palpation along the muscle-tendon unit, pain with resisted knee flexion and the inability to participate in sports activities. Recurrent injuries will be monitored weekly during the course of rehabilitation and at each follow-up study visit (1, 2, 3, 4 & 6 weeks, 6 months) and follow-up phone call (3, 4, 9 and 12 months).

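### Section 4.1 admits subjects who qualify through work or military training without sport, but the Aim 3 and Aim 4 endpoint definitions do not fully cover them and the Aim 3 outcome is worded in two ways

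*Combined protocol and SAP*

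**What the plan says.** **Who can enter.** Civilians need more than 100 hours a year of Level I or Level II activity, and Level II includes occupation: "Level II (racquet sports, skiing, manual labour occupations/heavy physical work) activities will be eligible for participation in this study". At the military site, the rule is that individuals "involved in military training that at least is equivalent to heavy physical work in the civilian subjects will be eligible to participate in the study". Neither route in section 4.1 asks for sport or for a sports injury. Section 1.2 describes the recruits as "military personnel, veterans or their families that have sustained an acute sports-related hamstring injury", but it also states the goal as healing after sports, military training or combat injuries. Section 6.1 accepts, at the military site, "grade II/III hamstring strains due to sports or duty related injury".

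**Aim 3 primary outcome.** Sections 7.2 (Effectiveness assessments) and 9.1.1 give "the number of days from injury to full, unrestricted return to practice". Section 6.4.2.1 gives "the number of days from injury to full, unrestricted return to practice or military training". Section 6.4.1 likewise clears subjects for practice or military activity. None of them mentions work.

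**Aim 4 recurrence.** Sections 6.4.2.1, 7.2 and 9.1.1 use the same list of joint criteria: a specific mechanism that brings back posterior thigh pain, tenderness along the muscle-tendon unit, and finally "pain with resisted knee flexion and the inability to participate in sports activities". Hypothesis 4 in section 2.1 concerns recurrence after return to sports and military activity.

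**The concern.** The entry criteria and the endpoints describe different populations. A labourer who plays no sport has no defined return event for Aim 3. A soldier has one in section 6.4.2.1 but not in the two other places where the same outcome is defined. For Aim 4, both kinds of subject face a final criterion stated only in terms of sport.

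Section 9.2 says the trial exists to observe trends and estimate effect sizes for later power calculations, and section 9.4 analyses recurrence as a yes/no outcome by logistic regression. If true re-injuries in non-sport subjects are scored negative, the recurrence rate passed to the next trial is too low. The sensitivity analysis in section 9.4 would not show this for recurrence. It reassigns scores for persons with missing information, whereas these subjects would carry a recorded negative. If instead each assessor decides what the criterion means for a non-player, the two sites may apply different rules.

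**Working it through.** **Step 1. Coverage by qualifying route, for a subject who plays no sport**

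| Qualifying route (4.1) | Aim 3 in 6.4.2.1 | Aim 3 in 7.2 and 9.1.1 | Aim 4 (all three places) |
|---|---|---|---|
| Sport | defined | defined | defined |
| Military training | defined | not named | sport only |
| Manual labour | not named | not named | sport only |

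Soldiers therefore have an inconsistency on Aim 3 and a gap on Aim 4. Labourers have a gap on both. Section 6.3.1 does record sports and work activity levels at screening, but no Aim 3 or Aim 4 endpoint uses the work measure.

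**Step 2. Scale for Aim 4**

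Inputs from the documents:
- expected control recurrence within one year, 50-60% (section 9.4)
- 20 subjects, 10 per group (section 9.2)

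Assumptions:
- a share f of subjects plays no sport (the documents give no mix)
- those subjects truly recur at the same rate as the others
- all of their recurrences are scored negative

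The last assumption is the literal reading, so the results are an upper limit for each f.

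Recorded rate = true rate × (1 − f):

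| f | Subjects of 20 | From 50% | From 60% |
|---|---|---|---|
| 10% | 2 | 0.50 × 0.9 = 45% | 0.60 × 0.9 = 54% |
| 20% | 4 | 0.50 × 0.8 = 40% | 0.60 × 0.8 = 48% |
| 30% | 6 | 0.50 × 0.7 = 35% | 0.60 × 0.7 = 42% |

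One misclassified recurrence in an arm of 10 changes that arm's rate by 1/10 = 10 percentage points.

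**Step 3. Effect on a later sample size**

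The plan gives no calculation to reproduce. Section 9.2 fixes N = 20 and states that power is insufficient. Further assumptions here are a halved risk on losartan (p2 = p1/2), two-sided alpha 0.05 and 80% power. With p̄ = (p1 + p2)/2,

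n per arm = [1.96·√(2p̄(1−p̄)) + 0.842·√(p1(1−p1) + p2(1−p2))]² / (p1 − p2)²

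| f | p1 vs p2 (true control rate 60%) | n | p1 vs p2 (true control rate 50%) | n |
|---|---|---|---|---|
| 0 | 0.60 vs 0.30 | 42 | 0.50 vs 0.25 | 58 |
| 10% | 0.54 vs 0.27 | 51 | 0.45 vs 0.225 | 69 |
| 20% | 0.48 vs 0.24 | 62 | 0.40 vs 0.20 | 82 |
| 30% | 0.42 vs 0.21 | 76 | 0.35 vs 0.175 | 99 |

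If f is the same in both arms, the expected risk ratio does not change, because the factor (1 − f) cancels. The risk difference shrinks by that factor. An unequal split of such subjects between the arms would also disturb the ratio.

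**The case against.** **The criterion can be read as a capacity.** An assessor may judge someone with a new mechanism, returned pain, tenderness and pain on resisted flexion to be unable to take part in sport, whether or not that person plays. This stands as a possible reading. It makes the text ambiguous, and the recurrence count would then rest on each site's judgement.

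**Re-injuries would still be seen.** Section 6.4.2.1 monitors all subjects at every visit and call and schedules a visit to confirm a re-injury, and section 8.2.1 asks about new injuries. This stands too: the risk is misclassification, not loss of data. However, the instruction to contact the coordinator is itself tied to return to sports participation.

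**Few subjects may be affected.** Civilians come from a sports medicine centre or athletic training rooms (section 4), and section 1.2 speaks of sports-related injury. This also stands. The share is unknown, and nothing in the documents shows that labourers without sport will be common.

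**The shift is small beside the pilot's imprecision.** With 5 recurrences among 10 subjects, the exact 95% interval is about 19% to 81%, and sections 9.2 and 9.4 already disclaim power. This stands as to size. Imprecision does not justify a definition that leans in one direction when correcting it costs almost nothing.

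**Stronger readings to avoid.** A reader might infer that non-sport subjects cannot reach either endpoint, so that Aim 3 is always missing and Aim 4 always zero for them. The documents do not support this. Section 6.4.2.1 gives soldiers an Aim 3 event, and a zero on Aim 4 follows from only one reading of the sports criterion. A reader might also infer that the error gathers at the military site. For Aim 3, under section 6.4.2.1, only subjects who qualify through work lack an event.

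**Conclusion.** The point holds as a mismatch between eligibility and endpoint wording. The Aim 3 primary outcome has two definitions, and neither covers return to work. The Aim 4 recurrence definition has no military or work equivalent, although section 4.1 admits such subjects and Hypothesis 4 names military activity. On the literal reading, a re-injured soldier or labourer who plays no sport could be scored as not recurred.

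The size is unknown and may be small. The recorded control rates of 45-54% down to 35-42% rest on an assumed 10% to 30% share and on every recurrence in that group being scored negative. The sample sizes in the working also need the assumed halved risk. The mismatch should be corrected, because the pilot's main product is the estimates it hands to the next trial. It does not undermine the trial, and it has no bearing on the Aim 1 safety assessment.

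**What to change.** 1. At screening, record each subject's qualifying activity or activities under section 4.1 (sport, occupation, military training). Where there are several, name one as primary.
2. Use one Aim 3 definition in sections 6.4.2.1, 7.2 and 9.1.1: days from injury until the subject is back, fully and without restriction, in the primary qualifying activity, whether practice, military training or work.
3. In the recurrence definition in the same three sections, replace the last element with inability to take part in the qualifying sport, military training or work activity.

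Narrowing section 4.1 to sports injuries is not a good substitute. It would conflict with the goal stated in section 1.2, which includes military training and combat injuries, and with the duty-related injuries accepted in section 6.1.

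The cost is wording in three sections and one case report form field, with no new visit or procedure. One small drawback is that return times would pool different kinds of activity. Summarising them by activity type as well deals with that.

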#### **4.2 Subject exclusion criteria**

Subjects will be excluded if they: 1) have had a previous hamstring injury on the same side or chronic symptoms; 2) have an injury that requires surgical intervention (e.g. avulsion with associated bony involvement, grade III complete tears); 3) have concurrent lower back symptoms; 4) are pregnant or breast feeding; 5) are a smoker; 6) have contraindications to Losartan therapy (e.g. known hypersensitivity to losartan, hepatic impairment); 7) currently use angiotensin I converting enzyme inhibitor (ACEI) / angiotensin II receptor blocker (ARB); 8) have hypertension (blood pressure greater than or equal to 140 mm Hg systolic pressure or greater than or equal to 90 mm Hg diastolic pressure); 9) have hypotension (blood pressure less than or equal to 90 mm Hg systolic pressure or less than or equal to 60 mm disastolic pressure); 10) have orthostatic hypotension defined as a drop in systolic pressure greater than or equal to 20 mm Hg or a drop in diastolic blood pressure greater than or equal to 10 mm Hg or reports of lightheadedness or dizziness would be considered abnormal upon standing or 11) have diabetes mellitus, cardio-vascular, renal or hepatic co-morbidities.

Additionally, because participation in this study requires undergoing MRI, subjects will be excluded if they: 1) had prior surgery for an aneurysm; 2) have a cardiac pacemaker; 3) have metal fragments in the eyes, brain or

spinal cord from shrapnel, metal work or welding; 4) have surgical implants, such as an ear implant or neurostimulator; 5) have a history of claustrophobia or 6) have a history of not tolerating previous MRI scans without medication.

For the military personnel, individuals recruited to participate in this study should not have a scheduled deployment within 6 months following initial injury to ensure adequate follow up.

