## **9.4        Effectiveness analysis**

The distribution of baseline characteristics and important prognostic factors (age, sex, body mass index, pre-injury activity level, etc) will be summarized overall, and by treatment (versus control) group to assess the effectiveness of the randomized allocation. Continuous variables will be summarized with means and standard deviations, and medians and inter-quartile ranges. Categorical data will be summarized using frequencies and percentages. We will then graphically explore the distributions of the primary outcome variables (for normality or skewedness and potential outliers) using q-q plots and histograms before conducting any tests to compare the two groups. When appropriate, transformations will be applied to outcome measures that are not normally distributed.

We anticipate minimal loss to follow-up (<5% of patients) at the 6 month assessment and only 10-15% loss to follow-up at 12 months post-injury. The primary outcome measures (safety and tolerance, recovery of muscle structure and function, return to prior level of function) will be evaluated between 6 weeks and 6 months; therefore the only outcome that could appreciably be affected by lost to follow-up is recurrence of injury within 12 months. We will compare baseline characteristics between participants and drop-outs, obtain reasons for

study drop (to investigate the possible missing data mechanism), and will also conduct a sensitivity analysis (assigning poor scores and good scores to those persons with missing information differentially by treatment assignment) to evaluate the impact on our study results.

For outcome variables that are measured repeatedly, we will use mixed models to adjust for correlation among the observations from the same person as well as a clustering effect for each site. In these models, subject characteristics such as age, sex, and treatment group will be fixed effect predictors, and subject and site identification will be included as random effects. Depending on the type of outcome variable of interest, we will employ linear mixed models or mixed effect logistic regression. Though we do not anticipate statistically significant differences between the Losartan and placebo groups due to the small sample size, these analyses will guide us in developing future clinical trials.

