For time to recurrence, which will be the focus of Specific Aim 4, we expect 50%-60% of subjects in control group will have recurrence within one year. Although the subjects will report whether they had recurrence or not at intermittent time points (3, 4, 6, 9 and 12 months after treatment), we will have subjects report the actual date of recurrence. We will perform logistic regression (recurred/not recurred), and if we obtain reliable information about recurrence date and we have enough number of recurrences, we will consider Cox regression model to investigate the effect of treatment on time to recurrence, though we do not anticipate having enough power to achieve statistically significant results with either logistic or Cox modeling.

Any deviations from the previously described statistical plan will be described and justified in a protocol amendment and/or in the final report submitted to the IND application.

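### The deployment exclusion protects 6 months of follow-up, but recurrence is a 12-month endpoint analysed yes/no, with no sound way to use subjects lost in between without a recurrence

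*Combined protocol and SAP*

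**What the plan says.** Section 4.2 limits military recruitment to protect follow-up: these subjects "should not have a scheduled deployment within 6 months following initial injury to ensure adequate follow up". A deployment scheduled later than that is allowed.

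The recurrence endpoint runs twice as long. Section 6.4.2.1 states: "Recurrence of injury will be monitored over the course of 12 months after study enrolment and randomization". Section 9.1.1 lists incidence of recurrence among the primary endpoints. After the 6-month visit, contact is by telephone at 9 and 12 months. A subject who reports a recurrence is asked to come in: "a return visit will be scheduled to confirm the presence and severity of re-injury".

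Section 9.4 gives the expected losses: "We anticipate minimal loss to follow-up (<5% of patients) at the 6 month assessment" and "only 10-15% loss to follow-up at 12 months post-injury". It names recurrence as the one outcome that loss could appreciably affect. It plans to compare drop-outs with participants, to collect reasons for leaving, and to run a sensitivity analysis that gives good and poor scores to missing subjects differentially by arm.

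For the control group, "we expect 50%-60% of subjects in control group will have recurrence within one year". Section 9.4 calls time to recurrence the focus of Aim 4 and has subjects report the actual date, but the committed model is binary: "We will perform logistic regression (recurred/not recurred"). Cox regression is only to be considered, if the dates prove reliable and there are enough recurrences. No rule says how the logistic model codes a subject who leaves before month 12 without a recurrence.

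**The concern.** The plan treats deployment as a threat to follow-up and then leaves the second half of the recurrence window uncovered. The definition of recurrence includes tenderness to palpation and pain on resisted knee flexion, so a deployed subject who answers the telephone may still be hard to confirm.

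The binary model makes this matter. A subject who recurs and then leaves already has an outcome. One who leaves recurrence-free at month 8 has contributed 8 months of information, but has no 12-month yes or no. The analyst must drop the subject or assign a value, and each choice gives a different rate. Section 9.2 says the trial exists to estimate effect sizes for future power calculations, and the control recurrence rate is an input to those.

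**Working it through.** **Inputs from section 9.4.** Control recurrence by 12 months, R = 50% or 60%. Loss by month 6, L6 = 5% (the plan says below 5%, so this is its upper edge). Loss by month 12, L12 = 10% or 15%.

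**Assumptions, not in the plan.** Constant recurrence hazard; loss independent of recurrence and spread evenly within each half-year; a recurrence before loss is known.

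**Step 1: average recurrence-free fraction in each half-year.** With S6 = (1 − R)^0.5:
- a1 = (1 − S6) / (−0.5 × ln(1 − R))
- a2 = S6 × a1

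R = 50%: S6 = 0.707, a1 = 0.845, a2 = 0.598. R = 60%: S6 = 0.632, a1 = 0.802, a2 = 0.507. Recurrence by month 6 is therefore 29.3% or 36.8%, which is 59% or 61% of the 12-month total.

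**Step 2: subjects lost without a recurrence.** U = L6 × a1 + (L12 − L6) × a2. For R = 50%, L12 = 15%: 0.05 × 0.845 + 0.10 × 0.598 = 0.102.

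**Step 3: recurrences seen.** O = 1 − U − (1 − L12)(1 − R). Same case: 1 − 0.102 − 0.85 × 0.50 = 0.473.

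**Step 4: three possible codings.**
- A, keep recurrences seen before loss and drop the rest of the lost: O / (1 − U) = 0.473 / 0.898 = 52.7%
- B, drop every lost subject: R, unbiased under independent loss, but it discards observed recurrences
- C, score the lost as not recurred: O = 47.3%

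| True R | Loss by month 12 | U | A | C |
|---|---|---|---|---|
| 50% | 10% | 7.2% | 51.5% (+1.5) | 47.8% (−2.2) |
| 50% | 15% | 10.2% | 52.7% (+2.7) | 47.3% (−2.7) |
| 60% | 10% | 6.5% | 61.5% (+1.5) | 57.5% (−2.5) |
| 60% | 15% | 9.1% | 62.6% (+2.6) | 56.9% (−3.1) |

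If the control rate applied to all 20 subjects, U means 1.3 to 2.0 people.

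**Sensitivity to the assumptions.** With 80% or 20% of recurrences before month 6, A overstates by 0.9 to 3.0 points and C understates by 1.8 to 5.1. With no loss by month 6 and 15% by month 12, constant hazard, A is +3.2 to +3.3 and C is −1.5 to −1.6. If deployment raised total loss to 35% (an assumption), A would be +8.3 or +7.8 and C −4.7 or −5.2.

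**Planned good/poor scoring.** Scoring all unscored subjects one way or the other at 15% loss spans 47.3% to 57.5% when the truth is 50%, and 56.9% to 66.0% when it is 60%.

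**Between-arm contrast.** Assume Losartan halves recurrence and loss is 15% in both arms. For 50% v 25%, the odds ratio of 0.333 becomes 0.332 (A) or 0.343 (C), and the risk difference of −25.0 points becomes −25.7 or −23.8. For 60% v 30%, the odds ratio of 0.286 becomes 0.284 or 0.298.

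**Time-to-event estimate.** Under the same independent loss, an estimate that censors at last contact targets the true 50% or 60%, with no coding choice to make.

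**The case against.** The plan has much of this in hand. Contact after month 6 is by telephone, so a reader who infers that deployed subjects cannot be scored goes beyond the documents: nothing says deployment ends contact, and a recurrence before departure is already recorded. The difficulty is confined to subjects who become unreachable or cannot attend confirmation.

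A reader might also infer that the logistic model overstates recurrence. That holds only under coding A; B gives no bias and C gives understatement, and the plan chooses none of them.

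Hypothesis 4 compares arms, deployment has no evident reason to differ between blinded arms, and equal loss barely moves the odds ratio. The error is also small beside sampling noise: for one arm of 10 at 55%, 1.96 × √(0.55 × 0.45 / 10) is about 31 points either way. The 6-month window does cover the last scheduled in-person visit and the follow-up MRI. Section 9.4 acknowledges the loss and brackets it, and its 10-15% may already include deployment.

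All of this limits the size. It does not supply a coding rule, and the bracketing describes uncertainty around a main estimate that remains undefined. Equal loss is an expectation only: if 2 of 20 subjects are unscored at random, the chance that both are in one arm is 9/19, or 47%.

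The doubt about self-reported dates has limited force. A Kaplan-Meier estimate at 12 months needs only the order of recurrences and censorings. Section 11.1 already sets an unrecalled day to the 15th of the month, an error of about two weeks.

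**Conclusion.** The point holds, at modest size. The deployment window is shorter than the recurrence endpoint, and the committed model cannot make sound use of partial follow-up. At the plan's own 10-15% loss, an arm's 12-month recurrence is overstated by about 1.5 to 2.7 points or understated by about 2 to 3, depending on an unstated coding. This rests on the 50-60% control rate, a constant hazard, independent loss, and 5% lost by month 6. The treatment odds ratio is hardly affected if loss is equal by arm. Heavier loss from deployment would widen the error, but the documents give neither a deployment rate nor the military share, so a large bias cannot be claimed from them. The point is worth acting on because a better estimate is available from dates the plan already collects.

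**What to change.** In section 9.4, make the main Aim 4 estimate the Kaplan-Meier 12-month recurrence in each arm, from randomization, with the between-arm difference and its confidence interval. Use the reported recurrence dates and censor at the last contact at which recurrence status was established. This needs no minimum number of events, unlike the conditional Cox model. Keep the yes/no logistic model, with its coding of lost subjects written down, and the good/poor scoring as sensitivity analyses.

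In sections 4.2 and 6.4.2.1, record at screening any deployment scheduled within 12 months, and bring the next recurrence and adverse-event call forward to before departure. Eligibility need not change.

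The cost is analysis wording, one screening item, and one rescheduled call per deploying subject. The downside is an assumption that censoring is unrelated to recurrence risk, which deployment could strain if it changes physical activity, and some reliance on self-reported dates. The retained good/poor scoring probes the first; the confirmation visit, where it takes place, helps with the second.
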